7.5.2 Assessment of Reference Standard against the ⁶⁴Cu-SAR-bisPSMA PET/CT Results

For the assessment of the Reference Standard against the ⁶⁴Cu-SAR-bisPSMA PET/CT, region-level matching will be used for histopathology, subregion-level matching for imaging and participant-level matching for PSA response to radiation or other salvage focal therapy (refer to Section 7.5.1). Matching of the Reference Standard against the ⁶⁴Cu-SAR-bisPSMA PET/CT results will be completed via statistical programming.

Assessment of **region-level** Reference Standard against the ⁶⁴Cu-SAR-bisPSMA PET/CT results:

- Histopathology: A region that is ⁶⁴Cu-SAR-bisPSMA PET-positive (i.e., includes at least one unequivocal PET-positive lesion) and Reference Standard positive, will be assigned as true positive (TP) for the region-level status.
- Imaging: A subregion that is ⁶⁴Cu-SAR-bisPSMA PET-positive (i.e., includes at least one unequivocal PET-positive lesion) and Reference Standard positive (i.e., includes at least one unequivocal lesion detected on conventional imaging in that subregion), will be assigned as TP. A region that includes at least one TP subregion will be assigned as TP for the region-level status.
- A region that is ⁶⁴Cu-SAR-bisPSMA PET-positive (i.e., includes at least one unequivocal PET-positive lesion) and is Reference Standard negative based on at least 1 evaluable timepoint, will be assigned as false positive (FP) for the region-level status.
- A region that is ⁶⁴Cu-SAR-bisPSMA PET-negative (i.e., no unequivocal PET-positive lesion or only equivocal lesion(s) detected within the subregions) and Reference Standard negative, will be assigned as true negative (TN) for the region-level status.
- A region that has either non-evaluable ⁶⁴Cu-SAR-bisPSMA result for a specific timepoint or has a non-evaluable or inconclusive Reference Standard will not be assigned for that timepoint.

Assessment of **participant-level** Reference Standard against the ⁶⁴Cu-SAR-bisPSMA PET/CT results:

- A participant with at least one TP region AND/OR at least one unequivocal ⁶⁴Cu-SARbisPSMA PET-positive lesion and confirmed PSA response to radiation or other salvage focal therapy, will be assigned as TP for the participant-level status.
- A participant with at least one unequivocal ⁶⁴Cu-SAR-bisPSMA PET-positive lesion who does not meet the above criteria to be deemed TP, will be assigned as FP for the participant-level status.

- A participant with a negative ⁶⁴Cu-SAR-bisPSMA PET/CT (i.e., no unequivocal PETpositive lesion or only equivocal lesion(s) detected on the scan) and negative Reference Standard, will be assigned as TN for the participant-level status.
- A participant that has either non-evaluable ⁶⁴Cu-SAR-bisPSMA result for a specific timepoint or has a non-evaluable or inconclusive Reference Standard will not be assigned for that timepoint.

False negative results (on a region- or participant-level) will not be assigned in the study. A participant with negative baseline conventional imaging and negative ⁶⁴Cu-SAR-bisPSMA PET/CT imaging, who later demonstrates a positive result at follow-up conventional imaging (e.g., during the 90-day follow-up imaging) will not be considered a false negative as there is no way to determine whether the disease was initially present, or whether the disease has developed since the acquisition of the baseline and ⁶⁴Cu-SAR-bisPSMA imaging. A positive follow-up scan must therefore be interpreted with caution as it may reflect a different disease state compared to the one evaluated during the baseline conventional and ⁶⁴Cu-SAR-bisPSMA PET/CT imaging period.

A positive ⁶⁴Cu-SAR-bisPSMA PET/CT within the target study population may indicate that this new imaging agent is more sensitive in detecting early recurrence than other available modalities. The 90- and 180-day follow-up timelines have been selected to allow for further development of the disease so the positive ⁶⁴Cu-SAR-bisPSMA PET/CT findings can be validated using conventional, potentially less sensitive reference modalities. The selected follow-up timelines therefore enable evaluation of the diagnostic efficacy endpoints that relate to positive findings, but do not allow for a reliable assessment of false negative results.

7.5.3 Disease Management Plan

The treating physician will be required to fill out a Pre-SAR-bisPSMA and a Post-SAR-bisPSMA Disease Management Form to provide information on the treatment strategy of the participant before and after the information from the local read of the ⁶⁴Cu-SAR-bisPSMA PET/CT scan(s) becomes available.

The Pre-SAR-bisPSMA Disease Management Form must be completed during Screening by the treating physician to document the initial intended management plan for the participant based on available clinical information and conventional imaging results.

The Post-SAR-bisPSMA Disease Management Form must be completed by the treating physician for all participants who complete the ⁶⁴Cu-SAR-bisPSMA PET/CT scan(s). This management plan will be based on the result from the local interpretation of the ⁶⁴Cu-SAR-bisPSMA PET/CT scan(s) to document whether a change to the initial intended management plan may be warranted due to the ⁶⁴Cu-SAR-bisPSMA PET/CT finding(s). Additionally, the operator will be asked to indicate which ⁶⁴Cu-SAR-bisPSMA PET/CT timepoint has influenced the assessment. If both timepoints influenced the assessment (whether for change or not) both should be selected.

7.6 Pharmacokinetics

7.6.1 Biodistribution of ⁶⁴Cu-SAR-bisPSMA

The biodistribution of ⁶⁴Cu-SAR-bisPSMA utilizing the PET/CT scans will involve the calculation of:

• Maximum and mean SUVs in lesion(s), visceral/soft tissue, bone;

• Lesion-to-background ratio.

All biodistribution measures will be assessed centrally, according to the study Imaging Review Charter to ensure a high and consistent level of quantification across all sites.

8 VISIT-SPECIFIC PROCEDURES

8.1.1 Screening Period (28 days, Visit 1)

The following assessments must be performed/obtained within the 28 days before the participant receives the ⁶⁴Cu-SAR-bisPSMA administration. Informed consent must be documented before any study-specific screening procedure is performed and may be obtained more than 28 days before the ⁶⁴Cu-SAR-bisPSMA administration. Results of SOC tests or examinations performed prior to obtaining informed consent and within 28 days (within 60 days for institutional SOC conventional scans) prior to the ⁶⁴Cu-SAR-bisPSMA administration may be used; such tests do not need to be repeated for Screening.

If the start date for the ⁶⁴Cu-SAR-bisPSMA administration extends beyond 28 days from the start of the Screening assessments (e.g. due to issues related to logistics), the Investigator in consultation with the Medical Monitor must determine if any Screening assessments need to be repeated.

Assessments to be completed:

- Informed Consent (Refer to Section 11.5)
- Inclusion/Exclusion (Refer to Section 4.1
- Demographics and Disease Characteristics (Refer to Section 7.1.1)
- Medical and Medication History (Refer to Section 7.1.2)
- Prior Cancer Treatments (Refer to Section 7.1.3)
- Body Weight and Height (Refer to Section 7.2.2)
- ECOG Status (Refer to Section 7.2.3)
- Hematology (Refer to Section 7.2.6)
- Biochemistry (Refer to Section 7.2.6)
- Coagulation (Refer to Section 7.2.6)
- eGFR (CKD-EPI) (Refer to Section 7.2.6)
- Serum Testosterone (Refer to Section 7.2.6)
- Total PSA (Refer to Section 7.2.6)
- Adverse Events (Refer to Section 9.1)
- Concomitant Medications (Refer to Section 6)
- SOC Conventional Scan (Refer to Section 7.3.1)
- Pre-SAR-bisPSMA Disease Management Form (Refer to Section 7.5.3)

8.1.2 ⁶⁴Cu-SAR-bisPSMA PET/CT Imaging

8.1.2.1 Day 0 (Visit 2)

Enrolled participants who meet all eligibility criteria will receive a single ⁶⁴Cu-SAR-bisPSMA administration followed by a PET/CT scan. Pre-dose assessments will be completed prior to the administration of ⁶⁴Cu-SAR-bisPSMA. Post-dose assessments will be completed as per the assessment windows specified below.

Assessments to be completed:

• Adverse Events (ongoing)

• Concomitant Medications (ongoing)

Pre dose

- Body Weight (Refer to Section 7.2.2)
- Physical Exam (Refer to Section 7.2.1)
- Vital Signs (Refer to Section 7.2.4)
- Duplicate 12-Lead ECG (Refer to Section 7.2.5)
- Urinalysis (Refer to Section 7.2.6)

⁶⁴Cu-SAR-bisPSMA Dose (Refer to Section 5.4 for dosing and administration details)

Post dose

- Vital Signs to be completed prior to the ⁶⁴Cu-SAR-bisPSMA PET/CT (Refer to Section 7.2.4)
- Duplicate 12-Lead ECG to be performed at 30 min (±10 min) post ⁶⁴Cu-SAR-bisPSMA administration (Refer to Section 7.2.5)
- ⁶⁴Cu-SAR-bisPSMA PET/CT to be performed at 1 to 4 hours post ⁶⁴Cu-SAR-bisPSMA administration (Refer to Section 7.3.2)

8.1.2.2 Day 1 (24 hours ± 6 hours Post Dose, Visit 3)

This visit is to take place approximately 24 hours after the ⁶⁴Cu-SAR-bisPSMA administration.

Assessments to be completed:

- Adverse Events (ongoing)
- Concomitant Medications (ongoing)
- ⁶⁴Cu-SAR-bisPSMA PET/CT (Refer to Section 7.3.2)

8.1.3 Safety Visit (Day 7 ± 2 days, Visit 4)

This visit is to take place 7 days (\pm 2days) after the ⁶⁴Cu-SAR-bisPSMA administration.

Assessments to be completed:

- Adverse Events (ongoing)
- Concomitant Medications (ongoing)
- Record Any Prostate Cancer Treatments (Refer to Section 7.1.4)
- Physical Exam (Refer to Section 7.2.1)
- Body Weight (Refer to Section 7.2.2)
- Vital Signs (Refer to Section 7.2.4)
- Hematology (Refer to Section 7.2.6)
- Biochemistry (Refer to Section 7.2.6)
- Coagulation (Refer to Section 7.2.6)
- eGFR (CKD-EPI) (Refer to Section 7.2.6)
- Urinalysis (Refer to Section 7.2.6)
- Additional Imaging/Histopathology (Refer to Section 7.3.3 and 7.4)
- Post-SAR-bisPSMA Disease Management Form (Refer to Section 7.5.3)

8.1.4 Follow-Up

8.1.4.1 Day 90 (Day 90 ± 15 days, Visit 5)

This visit is to take place 90 days (\pm 15 days) after the ⁶⁴Cu-SAR-bisPSMA administration. All participants must complete this visit, regardless of the ⁶⁴Cu-SAR-bisPSMA PET/CT results.

Participants who based on the central expert panel's interpretation of the follow-up conventional imaging completed during Visit 5 are deemed:

- **negative or equivocal for PC recurrence** must continue to Visit 6.
- **positive for PC recurrence** no further study visits are required.

Assessments to be completed:

- Record Any Prostate Cancer Treatments (Refer to Section 7.1.4)
- Total PSA (Refer to Section 7.5.3)
- Follow-up Conventional Imaging (Refer to Section 7.3.3)
- Record Any Additional Imaging/Histopathology (Refer to Section 7.3.3 and 7.4)

8.1.4.2 Day 180 (Day 180 ± 15 days, Visit 6)

This visit is to take place 180 days (\pm 15 days) after the ⁶⁴Cu-SAR-bisPSMA administration.

Only participants who were deemed negative or equivocal for PC recurrence based on the follow-up conventional imaging (as per the central expert panel's interpretation) completed during Visit 5 must complete Visit 6.

If the participant is not returning to Visit 6, but additional imaging/histopathology was acquired within 180 days (\pm 15 days) of Day 0, the relevant details must be recorded on the eCRF and information submitted to the central reading center.

Assessments to be completed:

- Record Any Prostate Cancer Treatments (Refer to Section 7.1.4)
- Total PSA (Refer to Section 7.5.3)
- Follow-up Conventional Imaging (Refer to Section 7.3.3)
- Record Any Additional Imaging/Histopathology (Refer to Section 7.3.3 and 7.4)

9 ADVERSE EVENT MONITORING

9.1 Adverse Events

An AE is defined as any untoward medical occurrence in a clinical investigation participant administered a pharmaceutical product, which does not necessarily have a causal relationship with this treatment. An AE can therefore be any unfavorable and/or unintended sign (including an abnormal laboratory finding), symptom, or disease temporally associated with the use of an investigational product, whether or not related to the investigational product. All AEs, including observed or volunteered problems, complaints, or symptoms, are to be recorded on the appropriate eCRF.

Adverse events should be recorded from the time of informed consent until the completion of the Safety Visit. Adverse events recorded before the administration of the investigational product will be classified as non-treatment emergent AEs. All AEs recorded after the investigational product administration will be classified as treatment-emergent AEs (TEAEs). Non-related AEs will only be reported and followed up until the Safety Visit. All related AEs are to be followed up until resolved or judged to be no longer clinically significant, or until they become chronic to the extent that they can be fully characterized. An assessment should be made at the last study-related visit for each patient. Certain long-term AEs cannot be followed until resolution within the settings of this protocol. In these cases, follow-up will be the responsibility of the treating physician. If during AE follow-up the case has progressed to the level of SAE, or if a new SAE is observed whose relationship to the study medication

cannot be ruled out, the situation must be reported by the Investigator becoming aware of the information.

Participants should be instructed to report any AE that they experience to the Investigator.

Wherever possible, a specific disease or syndrome rather than individual associated signs and symptoms should be identified by the Investigator and recorded on the eCRF. However, if an observed or reported sign or symptom is not considered a component of a specific disease or syndrome by the Investigator, it should be recorded as a separate AE on the eCRF. Additionally, the condition that led to a medical or surgical procedure (e.g., surgery, endoscopy, tooth extraction, transfusion) should be recorded as an AE, not the procedure. Adverse events should be entered into the eCRF within 5 days of reporting.

Clinically significant abnormal laboratory or other examination (e.g., ECG) findings that are detected during the study should be reported as AEs. The Investigator will exercise his or her medical and scientific judgment in deciding whether an abnormal laboratory finding, or other abnormal assessment is clinically significant. Clinically significant abnormal laboratory values occurring during the clinical study will be followed until repeat tests return to normal, stabilize, or are no longer clinically significant. Any abnormal test that is determined to be an error does not require reporting as an AE.

Any event that in the opinion of the Investigator is solely due to the underlying disease should not be reported as an AE.

9.1.1 Adverse Drug Reaction

All noxious and unintended responses to a medicinal product related to any dose should be considered an adverse drug reaction. "Responses" to a medicinal product means that a causal relationship between a medicinal product and an AE is at least a reasonable possibility; i.e., the relationship cannot be ruled out.

9.1.2 Unexpected Adverse Drug Reaction

An unexpected adverse drug reaction is defined as an adverse reaction, the nature or severity of which is not consistent with the applicable product information. For ⁶⁴Cu-SAR-bisPSMA, the reference safety information is included in the current IB. The reference safety information is reviewed yearly, and the periodicity of the review will be harmonized with the reporting period of the Development Safety Update Report.

9.1.3 Assessment of Adverse Events by the Investigator

The Investigator will assess the severity (intensity) of each AE according to Common Terminology Criteria for Adverse Events (CTCAE) criteria and will also categorize each AE as to its potential relationship to investigational product using the categories of related or not related.

9.1.3.1 Assessment of Severity

Severity of AEs will be graded according to the following definitions:

The Investigator will make an assessment of severity (intensity) for each AE and SAE reported during the study using the National Cancer Institute (NCI) CTCAE V5.0 criteria. The assessments will be based on the Investigator's clinical judgment. The severity of each AE and SAE recorded in the eCRF should be assigned to 1 of the following:

Mild (Grade 1):	Mild; asymptomatic or mild symptoms; clinical or diagnostic observations only; intervention not indicated.
Moderate (Grade 2):	Moderate; minimal, local or noninvasive intervention indicated; limiting age-appropriate instrumental ADL*.
Severe (Grade 3):	Severe or medically significant but not immediately life- threatening; hospitalization or prolongation of hospitalization indicated; disabling; limiting self-care ADL**.
Life-threatening (Grade 4):	Life-threatening consequences; urgent intervention indicated.
Fatal (Grade 5):	Death related to AE.

Abbreviations: ADL= Activities of Daily Living

*Instrumental ADL refers to preparing meals, shopping for groceries or clothes, using the telephone, managing money, etc.

**Self-care ADL refers to bathing, dressing and undressing, feeding self, using the toilet, taking medications, and not being bedridden.

9.1.3.2 Causality Assessment

The Investigator is obligated to assess the relationship between investigational product and the occurrence of each AE/SAE. The Investigator will use clinical judgment to determine the relationship to ⁶⁴Cu-SAR-bisPSMA. Alternative causes, such as natural history of the underlying diseases, concomitant therapy, other risk factors, and the temporal relationship of the event to the investigational product will be considered and investigated.

The causal relationship of the AE to the investigational product or study procedures should be assessed by the Investigator (or medically qualified delegate) using the following classifications:

- Related: An AE that follows a temporal sequence from administration of the investigational product, or for which possible involvement of the investigational product cannot be ruled out, although factors other than the drug, such as underlying diseases, concurrent medical conditions, concomitant drugs and concurrent treatments, are also possibly responsible.
- Not related: An AE that does not follow a temporal sequence from investigational product administration and/or that can reasonably be explained by other factors, such as underlying diseases, concurrent medical conditions, concomitant drugs and concurrent treatments.

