#### 9.15.1 Adverse Events

AEs will be coded to system organ class and preferred term according to MedDRA, version 25. Pretreatment AEs are defined as AEs that have an onset on or after the date the informed consent was signed but before the time of the first dose of study drug. Treatment-emergent adverse events (TEAEs) are defined as AEs that start or worsen after the first dose of Cu-SAR-bisPSMA.

All AEs with partial or missing dates and times will be considered treatment-emergent unless a partial start date and/or time indicates the AE began before the dose of Cu-SAR-bisPSMA or a stop date indicates the AE ended before the dose of Cu-SAR-bisPSMA.

Summaries will be provided for TEAEs, with the number and percentage of participants reporting each type of event presented. If a participant's reports the same preferred term more than once, it is counted only once within that category. Similarly, if a participant has AEs of two or more preferred terms under the same system organ class, then that patient only counts once for that system organ class. Furthermore, for a given summary, the preferred term will only be counted once at its worst severity and strongest relationship to study drug.

PC symptoms of special interest will be collected and summarized separately by body system.

The following summaries and listings for AEs will be provided:

- An overall summary table of AEs summarizing the number and percent of patients, in the following categories: any AE, any TEAE, TEAEs by highest severity grade, TEAEs by relationship to study drug (related, not related), any serious TEAE, TEAEs leading to discontinuation from the study, TEAEs leading to study drug withdrawal, any TEAEs with a fatal outcome.
- o Incidence of TEAEs by MedDRA system organ class and preferred terms.
- Incidence of TEAEs by MedDRA system organ class, preferred terms, and maximum severity grade.
- o Incidence of related TEAEs by MedDRA system organ class, preferred terms, and maximum severity grade.
- Incidence of TEAEs grade 3 or higher by MedDRA system organ class and preferred term.
- Incidence of related TEAEs grade 3 or higher by MedDRA system organ class and preferred term.
- Incidence of Serious Adverse Events by MedDRA system organ class and preferred term.

September 4, 2024 CONFIDENTIAL Page 37 of 46

- Incidence of related Serious Adverse Events by MedDRA system organ class and preferred term

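### The two causality categories are not mutually exclusive: an adverse event that also has a reasonable alternative explanation can meet both Related and Not related, and no rule says which prevails

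*Protocol*

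**What the plan says.** Protocol 9.1.3 has the investigator "categorize each AE as to its potential relationship to investigational product using the categories of related or not related". There is no third or intermediate category.

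Protocol 9.1.3.2 defines the two:

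- Related: the event "follows a temporal sequence from administration of the investigational product, or for which possible involvement of the investigational product cannot be ruled out". A closing qualifier keeps the event in this category when something besides the product, for instance a comorbidity or another treatment, might also have caused it.
- Not related: the event "does not follow a temporal sequence from investigational product administration and/or that can reasonably be explained by other factors".

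The same section introduces the definitions with "The Investigator will use clinical judgment to determine the relationship to" the product, and asks that alternative causes and timing be looked into.

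Protocol 9.1.1 sets the standard for an adverse drug reaction: a causal link is at least reasonably possible, that is, "the relationship cannot be ruled out". Protocol 9.3.1 treats a related SAE and an adverse reaction as the same thing when it describes reporting to the authorities.

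The classification is used in three places:

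- Follow-up (Protocol 9.1): "Non-related AEs will only be reported and followed up until the Safety Visit", whereas related events are followed to resolution or until they no longer matter clinically or are chronic and characterized.
- Reporting (Protocol 9.3.1): an SAE judged related and unexpected goes on to the authorities.
- Tables: Protocol 10.4.4.1 tabulates related TEAEs and related TEAEs of grade 3 or higher. SAP 9.15.1 plans "TEAEs by relationship to study drug (related, not related") and adds a table of related SAEs.

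**The concern.** Two categories that are meant to split all adverse events must be exclusive and exhaustive. Here each is built from alternatives, and the alternatives collide. The Related definition says that another possible cause does not take an event out of that category. The Not related definition, through its and/or, lets a reasonable other explanation put the event in the opposite category on that ground alone.

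Take a man with known hypertension who has headache and raised blood pressure three hours after injection. The event follows the dose, so he meets Related. It can reasonably be put down to his existing condition, so he meets Not related. Two sites could record the same event in opposite ways and both be within the protocol. The related counts would then partly reflect site habit, and the follow-up and onward-reporting rules that hang on the classification would vary in the same way.

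**Working it through.** No rate, sample size or power figure is involved, and the plan states no figure to reproduce. The check is logical. Let

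- T = the event follows a temporal sequence from dosing;
- C = product involvement cannot be ruled out;
- E = the event can reasonably be explained by other factors.

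From Protocol 9.1.3.2: Related = T or C. Not related = (not T) or E, because and/or makes each part sufficient. From Protocol 9.1.1: adverse reaction = C.

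| T | C | E | Related | Not related | 9.1.1 standard |
|---|---|---|---|---|---|
| yes | yes | yes | met | met | reaction |
| yes | yes | no | met | – | reaction |
| yes | no | yes | met | met | not a reaction |
| yes | no | no | met | – | not a reaction |
| no | yes | yes | met | met | reaction |
| no | yes | no | met | met | reaction |
| no | no | yes | – | met | not a reaction |
| no | no | no | – | met | not a reaction |

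Four of the eight combinations meet both definitions, two meet only Related, two meet only Not related, and none falls outside both. The definitions are exhaustive but not exclusive. The rows are logical cases, not equally likely ones, so four of eight is not an estimate of how many events are affected.

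Three of the four overlapping rows have C. In those, 9.1.1 calls the event a reaction while 9.1.3.2 still permits Not related. In the fourth, the product has been excluded, yet timing alone still permits Related.

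Nothing elsewhere breaks the tie:

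- Timing and alternative causes, which 9.1.3.2 asks the investigator to weigh, are the two factors on which the definitions collide.
- SAP 9.15.1 counts a preferred term at its strongest relationship. That chooses among repeat reports of one term and does not classify a single event.
- SAP Table 3, which lists departures from the protocol analyses, does not mention causality.

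The size in the tables depends on how many events overlap, and the documents give no adverse event rate. As an illustration only, assume that 5 to 10 of 50 dosed participants had TEAEs and that all of these were of the overlapping kind. The related-TEAE incidence from them could then be 0/50 = 0% if all were called Not related, or 5/50 = 10% to 10/50 = 20% if all were called Related. Total TEAE incidence would be the same either way.

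**The case against.** The case on the other side is that the definitions are read under clinical judgment and not as a truth table. They also differ in degree: a factor that is possibly responsible is weaker than one that reasonably explains the event. The Related definition already contains the 9.1.1 test almost word for word, and 9.3.1 equates related with an adverse reaction, so the documents lean toward Related in doubtful cases. The related tables are descriptive cuts in a single-arm study without formal hypothesis testing, and every adverse event is tabulated and listed regardless of causality.

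Much of this stands and limits the point. A reader might infer the following, which the documents do not support:

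- That the primary safety result is in doubt. Its endpoint in Protocol 2.7.1 counts all treatment-emergent AEs and SAEs, with no condition on relatedness.
- That SAEs could go unreported or be dropped at Day 7. Protocol 9.3.1 sends every SAE up to the Safety Visit to the sponsor within 24 hours, and 9.3.2 follows each SAE whatever its cause. The medical monitor reviews SAE reports in real time (4.6).
- That all non-related findings stop at Day 7. Clinically significant laboratory abnormalities are followed under 9.1 and 7.2.6 regardless.
- That causality is arbitrary, or that every post-dose event, such as a fall on Day 5, must be Related. That needs temporal sequence to mean mere onset after dosing, and needs the required judgment to be ignored.
- That the related share could run from 0% to 100%. That is only the logical bound within a group already defined as ambiguous.

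What does not stand is the claim that judgment or the difference in degree settles the overlap. The same comorbidity can be both possibly responsible and a reasonable explanation. A lean toward Related that is never written into the Not related definition is not a precedence rule.

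**Conclusion.** The point holds as a contradiction between stated rules. As written, the two categories in Protocol 9.1.3.2 overlap, and no precedence is given in the protocol or the SAP. Letting a reasonable alternative explanation suffice for Not related also conflicts with the standard in 9.1.1, which 9.3.1 ties to relatedness.

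What inherits the ambiguity is limited to:

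- the related-TEAE, related grade 3 or higher and related-SAE tables;
- the related/non-related follow-up split, for non-serious, non-laboratory events still ongoing at the Safety Visit;
- onward reporting of unexpected related SAEs, where the sponsor also takes a view.

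The classification is undetermined for overlapping events only. Their share of all TEAEs cannot be estimated from the documents; the range in the illustration is an assumption. The conclusion rests on reading and/or in its ordinary sense, so that either part is enough. This should be corrected, but it does not undermine the primary safety analysis.

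**What to change.** Reconcile Protocol 9.1, 9.1.1, 9.1.3.2 and 9.3.1 so that the two categories are exclusive and exhaustive under the protocol's own 9.1.1 standard:

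- Related: product involvement cannot be ruled out, even if other factors may have contributed.
- Not related: product involvement can be ruled out.
- Timing and alternative causes are evidence for that judgment and are not criteria in their own right.

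In the notation above, Related becomes C and Not related becomes not C, so each of the eight rows falls in exactly one category. A version that made plausible timing a condition of Related would not serve, because 9.1.1 has no such condition. Nor would a version that required either implausible timing or an identified other cause for Not related: an event with plausible timing, the product excluded and no other cause found would fit neither category.

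For events already recorded, add a listing of post-dose TEAEs classed Not related, with the recorded alternative cause where available, and state the ambiguity in the study report.

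The cost is protocol wording, eCRF guidance and a short note to sites. The related count may rise slightly where sites have relied on the alternative-explanation criterion.
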